# 8.4.2.3 Confirmatory statistical test strategy

Separate statistical test strategies will be conducted for the United States and Europe as outlined below

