# 8.4.3 Subgroup Analyses

Countries will be combined into regions US vs. Europe vs. rest of the world in order to define regional subgroups.

Subgroup analyses will include forest plots as well as treatment-interaction analyses, both for the region subgroups as well as further subgroups (e.g. based on stratification factors and/or baseline characteristics) and will be provided both for the primary efficacy endpoint as well as other relevant efficacy and/or safety endpoints. The treatment-interaction analysis will be conducted for the primary efficacy endpoint (PFS), and the secondary efficacy endpoints time to worsening of DRS-P and time to improvement in DRS-P.

09 FEB 2023 Page: 98 of 151

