## **13.7 Amendment 12**

## 13.7.1 Overview of changes

Amendment 12 is dated 09 FEB 2023.

Section(s)	Description of change	Rationale
Synopsis 4. Study design 5.2.1.2 Withdrawal from follow-up period 7.1.1 Tabulated overview 7.1.2.5.3 Survival follow- up 8.4.2.2 Secondary efficacy parameters	Survival follow-up period extended up to 7 years after the last patient started study treatment.	The extension of survival follow-up period from 3 years up to 7 years would allow long-term assessment of OS as both a safety and efficacy endpoint. The follow-up period may be extended based on emerging clinical data by the sponsor after consultation with the investigators and notification of IECs / IRBs. Once the study is analyzed for survival at 7 years after the last patient started study treatment, any patients still on treatment may continue to be treated under a separate provision to be determined.
Synopsis 3. Investigator and other study personnel 4. Study design 7.1.1 Tabulated overview 7.1.2 Timing of assessment 7.3 Efficacy 7.5.3 Further safety 7.6.2 Quality of life questionnaire 7.6.3 Electronic patient reported outcomes evaluation (deleted section) 12. Reference list 14.5 Quality of life questionnaire: FLymSI-18	Reduced efficacy and safety assessments:  Central assessment of tumor images will no longer be performed  Central assessment of bone marrow biopsy will no longer be performed  No further data collection is required for the QoL questionnaires  Glucose and blood pressure measurements required prior to copanlisib/placebo infusion  Urinalysis no longer required	Study 17067 achieved primary completion as well as 1-year and 2-year follow-up. The study met its primary endpoint and, therefore, central review of tumor images is no longer deemed necessary. In addition, sufficient PRO data have been collected for the analyses in this study, and no further data collection is considered necessary. Some safety assessments have also been simplified to decrease patient burden, since the safety profile of copanlisib in combination with rituximab was established and is known by the investigators (i.e., reduction in blood pressure and glucose assessment frequency, and removal of urinalysis assessment).
6.2 Identity of investigational medicinal products	Added guidance for study drug storage, accountability, reconciliation, and record maintenance	Clarification to comply with the requirement of the EU CTR 536/2014.

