This Statistical Analysis Plan (SAP) Supplement 3 is used for the analyses of 3-year follow-up after the primary completion. The data cut-off date is 31 AUG 2023. Evaluations of selected analyses will be performed using data up to the cut-off date.

The analyses performed 2 years after the primary completion will be repeated in this analysis plan. All subgroup analyses for the time to event endpoints will be done on non-stratified Cox model and log-rank test.

There are a few changes in this 3-year follow-up analysis after the primary completion:

- To align with the latest TransCelerate clinical study report (CSR) template, Section 14 (TLFs) and Section 16.2 (Listings) will be renumbered to Section 8 and Section 10.2. In addition, subject listings listed below in the original Section 14 will be moved to the new Section 10.2.
 - Subject listing, subjects with COVID-19 related protocol deviations in Section 14 1 1
 - O Subject listing, copanlisib/placebo: dose delay ≥60 days due to COVID-19 in Section 14.2.1
 - o Section 14.3.2, listing of deaths, other serious and significant AEs
 - Section 14.3.3, listing of pregnancy test
- As the number of death events increases, the following subgroup analysis will be conducted for the efficacy endpoint overall survival (OS). Forest plot of the hazard ratios will be provided.
 - o iNHL histology (FL vs. other iNHL histology)
 - Entry criterion (progression-free and treatment-free interval following the last rituximab-containing treatment ≥ 12 months vs. considered unwilling/unfit to receive chemotherapy for age or comorbidities)
 - o Presence of bulky disease (yes vs. no)
 - o Previous treatment with PI3K inhibitors (yes vs. no)
 - o Prior lines of systemic anti-cancer therapy (1 vs. 2 vs. 3 vs. \geq 4)
 - o Age ($<65 \text{ vs.} \ge 65$)
 - o ECOG performance status (0 vs. 1 vs. 2)
- Subgroup analyses for time to deterioration in DRS-P of at least 3 points, and time to improvement in DRS-P of at least 3 points will not be performed as sufficient patient-reported outcome (PRO) data analyses have been provided.
- Summary of participants with cytomegalovirus (CMV) infections will be displayed descriptively.

2. References

(1) Statistical Analysis Plan, version 6.0, BAY 80-6946 / 17067, dated 26 AUG 2020

Protocol No.: **BAY 80-6946 / 17067**

(2) Statistical Analysis Plan TLF Specifications, version 1.0, BAY 80-6946 / 17067, dated 14 SEP 2020

Page: 5 of 5

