All the analyses performed one year after the primary completion will be repeated in this analysis plan. The details of the analyses are described in the main SAP, version 6.0, dated 26 AUG 2020 for the analyses at the primary completion, and SAP Supplement, version 1.0, dated 02 AUG 2021 for the analyses at one year after the primary completion. The list of tables and figures will be identical to the ones in TLF Specifications Supplement, version 1.0, dated 02 AUG 2021. The layout and specifications of the tables and figures will be the same as in the main TLF Specifications, version 1.0, dated 14 SEP 2020. No new TLF Specification document will be prepared for this analysis plan.

2. References

- (1) Statistical Analysis Plan, version 6.0, BAY 80-6946 / 17067, dated 26 AUG 2020
- (2) Statistical Analysis Plan TLF Specifications, version 1.0, BAY 80-6946 / 17067, dated 14 SEP 2020
- (3) Statistical Analysis Plan Supplement, version 1.0, BAY 80-6946 / 17067, dated 02 AUG 2021
- (4) Statistical Analysis Plan TLF Specifications supplement, version 1.0, BAY 80-6946 / 17067, dated 02 AUG 2021

Protocol No.: **BAY 80-6946 / 17067** Page: 1 of

Title page

A Phase III, randomized, double-blind, placebo-controlled study evaluating the efficacy and safety of copanlisib in combination with rituximab in patients with relapsed indolent B-cell non-Hodgkin's lymphoma (iNHL) – CHRONOS -3

(Version 7.0, dated 22 MAY 2020)

SAP (incl. Version no. and date):

SAP for study 17067, Version 6.0, dated 26 AUG 2020

Clinical study III Date: 02 AUG 2021

phase:

Study No.: 17067 **Version:** 1.0

Author:

Confidential

The information provided in this document is strictly confidential and is intended solely for the guidance of the clinical investigation. Reproduction or disclosure of this document, whether in part or in full, to parties not associated with the clinical investigation or its use for any other purpose without the prior written consent of the sponsor is not permitted.

Throughout this document, symbols indicating proprietary names (®, TM) are not displayed. Hence, the appearance of product names without these symbols does not imply that these names are not protected.

This Statistical Analysis Plan is produced on a word-processing system and bears no signatures.

The approval of the Statistical Analysis Plan is documented in a separate Signature Document.

Protocol No.: BAY 80-6946 / 17067	Page: 2 of 6
Table of Contents	
Title page	1
Table of Contents	2

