6.2 Efficacy

Primary analysis based on the independent assessment on the primary efficacy endpoint progression-free survival (PFS) will be conducted. Analysis of PFS based on the investigator's assessment will also be conducted.

Overall survival (OS) will be analyzed using the data up to AUG 2021. For other secondary efficacy endpoints, i.e., tumor objective response rate (ORR), complete response rate (CRR), disease control rate (DCR), duration of response (DOR), and time to progression (TTP), analyses based on the independent assessment and investigator's assessment will be provided.

Analysis of time to deterioration and time to improvement in DRS-P at least 3 points will be performed.

Protocol No.: **BAY 80-6946 / 17067** Page: 5 of 6

Subgroup analysis by histology subgroup will be conducted for PFS, OS, ORR, CRR, DCR, DOR, and time to deterioration and time to improvement in DRS-P at least 3 points.

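### Should the new overall survival subgroup list in SAP Supplement 3 also include region?

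*SAP*

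**What the plan says.** Protocol Section 8.4.3 defines region: "Countries will be combined into regions US vs. Europe vs. rest of the world in order to define regional subgroups". It then provides for "forest plots as well as treatment-interaction analyses, both for the region subgroups as well as further subgroups", the further ones being given only as examples drawn from the stratification factors and baseline characteristics. On endpoints, it says these "will be provided both for the primary efficacy endpoint as well as other relevant efficacy and/or safety endpoints". It then limits the interaction analysis to progression-free survival and the two DRS-P times.

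The Introduction of SAP Supplement 3 adds the survival subgroups: "As the number of death events increases, the following subgroup analysis will be conducted for the efficacy endpoint overall survival (OS" and so on. The list is histology, entry criterion, bulky disease, previous PI3K inhibitor, prior lines, age and ECOG status, with a forest plot of hazard ratios. Supplement 3 uses an unstratified Cox model and log-rank test for all time-to-event subgroups.

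The earlier supplements do not bring region in. Supplement 1, Section 6.2, says: "Subgroup analysis by histology subgroup will be conducted for PFS, OS, ORR, CRR, DCR, DOR". Supplement 2 says: "All the analyses performed one year after the primary completion will be repeated in this analysis plan".

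**The concern.** Region is the only split whose levels are written out in Section 8.4.3 itself, and it is missing from the one place where the follow-up plan widens the survival subgroups. Supplement 3 gives a reason for dropping the DRS-P subgroups but none for leaving out region. The list also came after the primary, 1-year and 2-year analyses, when an unexplained choice of subgroups invites questions.

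Two features of the protocol seem to raise the stakes. Section 8.4.2.3 says "Separate statistical test strategies will be conducted for the United States and Europe as outlined below", which suggests that regional results matter. Section 13.7.1 says the longer follow-up "would allow long-term assessment of OS as both a safety and efficacy endpoint". If survival did differ by region, rows defined by factors unrelated to region would sit near the overall hazard ratio and would not show it.

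**Working it through.** No figure in the plan needs reproducing, so the check compares the texts and then asks what the extra rows could deliver.

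**1. Is region absent?** Yes. The seven factors give 2 + 2 + 2 + 2 + 4 + 2 + 3 = 17 rows, none of them region. Supplements 1 and 2 carry survival by histology only.

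**2. Does the protocol require region for survival?** Not expressly. Section 8.4.3 names progression-free survival and leaves the other endpoints to judgement. It does not say that every subgroup applies to every endpoint, or that the set is repeated at each later data cut. Section 8.4.2 ties the efficacy analyses to the point at which at least 190 PFS events have been observed. Section 8.4.2.2 separately provides for a follow-up survival analysis and leaves its details to the SAP. Choosing survival subgroups in a supplement is within that delegation.

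**3. Is the chosen list odd?** No. Section 8.4.3 offers stratification factors and baseline characteristics as its examples. All four stratification factors, whose levels are set in Section 6.3, are listed, with three clinical characteristics added. The list expands on the histology-only plan of Supplement 1.

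**4. Do the regional test strategies create a need?** No. In Section 8.4.2.3 the United States hierarchy tests the full analysis set and then the combined FL and MZL population. The European hierarchy tests the full analysis set throughout. Both use patients from all regions, and survival appears in neither.

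**5. How precise would region rows be?** The documents give neither the number of deaths nor the regional shares. I assume 80 to 160 deaths, 20% to 40% of them in a given region, and deaths split about 2:1 by arm. Then SE(log HR) = sqrt(1 / ((2/3)(1/3)d)) = sqrt(4.5/d) for d deaths in the row. The 95% interval runs from HR ÷ F to HR × F, with F = exp(1.96 × SE). If the true HR were 0.80 everywhere, the chance that a row shows HR above 1 is Φ(ln 0.80 / SE) = Φ(−0.223 / SE).

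| Deaths (assumed) | Region share (assumed) | d | SE | F | Chance HR > 1 |
|---|---|---|---|---|---|
| 80 | 20% | 16 | 0.530 | 2.8 | 34% |
| 120 | 20% | 24 | 0.433 | 2.3 | 30% |
| 120 | 40% | 48 | 0.306 | 1.8 | 23% |
| 160 | 40% | 64 | 0.265 | 1.7 | 20% |

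So, with an identical benefit everywhere, a region of this size would appear to favour placebo in roughly one in five to one in three repetitions.

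**6. Is anything lost for good?** No. The region levels stand in Section 8.4.3, country is coded in every patient number (Section 5.3), and Supplement 3 fixes the subgroup model. A later request for survival by region could be met without a new analytical choice.

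**The case for a change.** The best argument for a change is that Supplement 3 itself picks survival for a subgroup forest plot, so it can hardly be called not relevant in the sense of Section 8.4.3. It is awkward to include the splits that section merely offers as examples and omit the one it spells out. The amendment log (Section 13.1.1.6) shows that the region definition was added deliberately, with a regulatory subgroup guideline in mind. Imprecision does not single region out either: the rows for ECOG 2 or for previous PI3K inhibitor use may be smaller. One line in the supplement would settle the matter.

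Most of this is fair. The mismatch is real, the silence is untidy, and noise alone would not justify leaving region out while keeping other small rows. What does not stand is the step from untidy to wrong. The protocol leaves the choice open, and nothing in the documents suggests that region was left out because of what the data showed. That rows unrelated to region would hide a regional difference is true by construction and is no evidence that such a difference exists. There is also no open question about interaction tests for survival, because Section 8.4.3 confines them to other endpoints.

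**Conclusion.** The observation is correct and the plan can stand. This is a minor difference in alignment between protocol and SAP, within discretion the protocol grants. Following Supplement 3 as written gives sound survival results, overall and in the listed subgroups. Adding region would supply three exploratory rows for a supportive endpoint and would change no alpha, power, model or conclusion.

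The judgement rests on reading the reference to other relevant endpoints in Section 8.4.3 as discretionary, and on Section 8.4.2.2 leaving the follow-up survival details to the SAP. The main SAP version 6.0 and the TLF Specifications are cited but were not available. They may already deal with region, so the absence of a reason is established only for the supplements. The precision figures depend on the assumed numbers of deaths and regional shares; the textual conclusion does not.

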6.1 Population characteristics	
6.2 Efficacy	
6.3 Safety	
6.3.1 Adverse Events (AEs)	
6.3.2 Adverse Event Groupings	5
6.3.3 Clinical Laboratory Parameters	6
Table of Tables	
Table 6–1: Adverse Event Groupings	5
Table of Figures	

No table of figures entries found.

Protocol No.: **BAY 80-6946 / 17067** Page: 3 of 6

List of Abbreviations

AEs Adverse events

CRR Complete response rate

CTCAE Common Terminology Criteria of Adverse Event

DCR Disease control rate
DOR Duration of response

DRS-P Disease-related symptoms - physical

Medical Dictionary for Regulatory Activities

MLG MedDRA labelling group NCI National Cancer Institute ORR Objective response rate

OS Overall survival

ODWG Organ Dysfunction Working Group

PFS Progression-free survival
SAP Statistical Analysis Plan
SMQ Standardized MedDRA Query
TEAEs Treatment-emergent adverse events
TLF Tables, Listings, and Figures

TTP Time to progression

Protocol No.: **BAY 80-6946 / 17067** Page: 4 of 6

1. Introduction

This Supplement Statistical Analysis Plan (SAP) is used for the analyses one year after the primary completion. The data cut-off date will be AUG 2021. Evaluations of selected analyses in all sections will be performed using data up to the cut-off date.

This Supplement SAP version 1.0 is a supplement of SAP version 6.0 dated 26 AUG 2020. A list of tables and figures to be generated based on this SAP will be provided in a separate document (TLF specifications supplement). The layout and specifications of the tables and figures will be the same as in the main TLF specifications version 1.0, dated 14 SEP 2020.

2. Study Objectives

Refer to main SAP, Version 6.0 dated 26 AUG 2020.

3. Study Design

Refer to the main SAP v6.0 dated 26 AUG 2020.

4. General Statistical Considerations

Refer to the main SAP v6.0 dated 26 AUG 2020.

5. Analysis Sets

Refer to the main SAP v6.0 dated 26 AUG 2020.

6. Statistical Methodology

6.1 Population characteristics

Analyses on disposition, concomitant medication, and treatment duration and exposure will be performed.

Analysis of time to end of study treatment will be conducted. Kaplan-Meier plot for 'Time to end of study treatment' will be provided by treatment group, and by histology subgroup.

Treatment duration and dosage will be summarized for overall safety population and by histology subgroup.

6.2 Efficacy

Primary analysis based on the independent assessment on the primary efficacy endpoint progression-free survival (PFS) will be conducted. Analysis of PFS based on the investigator's assessment will also be conducted.

Overall survival (OS) will be analyzed using the data up to AUG 2021. For other secondary efficacy endpoints, i.e., tumor objective response rate (ORR), complete response rate (CRR), disease control rate (DCR), duration of response (DOR), and time to progression (TTP), analyses based on the independent assessment and investigator's assessment will be provided.

Analysis of time to deterioration and time to improvement in DRS-P at least 3 points will be performed.

Protocol No.: **BAY 80-6946 / 17067** Page: 5 of 6

Subgroup analysis by histology subgroup will be conducted for PFS, OS, ORR, CRR, DCR, DOR, and time to deterioration and time to improvement in DRS-P at least 3 points.

6.3 Safety

6.3.1 Adverse Events (AEs)

Analyses of adverse events for overall safety population and by histology subgroup will be conducted. In addition, the following subgroup analyses of AEs including death will be conducted by baseline renal function and baseline hepatic function using National Cancer Institute's Organ Dysfunction Working Group (NCI-ODWG) criteria:

- Overview of treatment-emergent AEs (TEAEs)
- Incidence rates of TEAEs
- Incidence rates of treatment-emergent serious AEs
- drug-related TEAEs (copanlisib/placebo or rituximab-related)
- TEAEs leading to treatment (copanlisib/placebo or rituximab) discontinuation
- Summary of deaths

6.3.2 Adverse Event Groupings

The table below presents definitions of adverse event groupings. The overall strategy for the MedDRA Searches is aimed at achieving high specificity. Wherever considered appropriate, narrow versions of SMQs will be used. Additional Bayer-specific MedDRA search groups will be used for searches where SMQs would not adequately cover the targeted search. The Bayer-specific MedDRA search groups include MedDRA Labelling Groupings (MLG). These groupings are created and centrally maintained by a dedicated coding group, according to requests by end-users from the medical and statistical functions. They are therefore potentially subject to change e.g. through MedDRA up-versioning.

Table 6-1: Adverse Event Groupings

Adverse Event Grouping	MedDRA Search criteria
Arterial hypertension	MLG: Hypertension
Hyperglycemia	MLG: Hyperglycemia
Non-infectious pneumonitis	SMQ: Interstitial lung disease (narrow, i.e. category 2A)

For each of the above listed groupings of adverse events, the following will be presented for treatment-emergent events and copanlisib/placebo-related treatment-emergent events:

- Incidence proportions, by worst CTCAE grade, by seriousness, by outcome, and by action taken; 95% Clopper Pearson (exact) confidence interval for the overall incidence proportion and for the category of serious adverse events.
- Incidence proportions by the specific reported preferred terms (within each grouping)
- Exposure-adjusted incidence rate, which is defined as the number of patients with the specific event divided by the sum of exposure-time among the patients in the study group; 95% exact confidence interval for the overall rate (assuming the first occurrences of an event follow a Poisson process with constant rate). Exposure time is defined as follows: if

Protocol No.: **BAY 80-6946 / 17067**

the event occurred, exposure time is the time to first occurrence of the event. If the event did not occur, then exposure time is the treatment duration plus time at risk after treatment end, where time at risk is the minimum of 30 days and day of death relative to last treatment.

Page: 6 of 6

6.3.3 Clinical Laboratory Parameters

Summary tables for clinical laboratory parameters for overall safety population will be provided.
